**Table 6.2. Baseline and Post-Baseline Definitions and Patient Population by Study Period and Type of Analysis**

Study Period/Analysis	Patient Population	Baseline Observations	Post-Baseline Observations
Lead-In Period			
TEAEs	All Enrolled Patients	Prior to first dose of open-label insulin lispro (or Visit 2 date if the dose date is missing)	The entire lead-in period after first dose of open-label insulin lispro and prior to the first dose of IP (or Visit 8 date if the dose date is missing).
Basal, prandial, and total insulin doses, and prandial/total insulin dose ratios continuous analysis	All Randomized Patients	Visit 2	Visits 3 to 8 prior to initiation of IP
Weight MMRM and ANCOVA	All Randomized Patients	Last of Visits 1-2	Visits 3–8 AND Last of Visits 3-8
26-Week Treatment Period (including Safety Follow-Up Visit where applicable)			
HbA1c MMRM and ANCOVA	All Randomized Patients with a baseline and at least 1 post-baseline observation while on IP	Last of Visits 7-8	Visits 11, 13, 15, and 18 prior to discontinuation of IP AND Last of Visits 9-18 prior to discontinuation of IP
HbA1c categorical analyses longitudinal logistic regression and LOCF logistic regression	All Randomized Patients with a baseline and at least one post-baseline observation while on IP	Last of Visits 7-8	Visits 11, 13, 15, and 18 prior to discontinuation of IP AND Last of Visits 9-18 prior to discontinuation of IP
1-hr and 2-hr PPG and other MMTT variables	All Randomized Patients with a post-baseline observation while on IP	Visit 8 prior to initiation of IP	Visit 18 prior to discontinuation of IP
10-point SMBG, basal, prandial insulin doses, prandial/total insulin dose ratios	All Randomized Patients with a baseline and at least one post-baseline observation	Visit 8 prior to initiation of IP	Visits , 15, and 18 prior to discontinuation of IP AND Last of Visits 9-18 prior to discontinuation of IP

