IWRS	X	X	X	X	X	X	X	X	X	X	X	X	X	X	X	X	X	X	X	X
Patient eligibility review	X																			
Randomization ^c								X												
Clinical Assessments																				
Patient demographics	X																			
Medical history and preexisting conditions	X																			
Physical exam/height ^d	X																			
Concomitant medication	X	X	X	X	X	X	X	X	X	X	X	X	X	X	X	X	X	X	X	X
AEs and product complaints	X	X	X	X	X	X	X	X	X	X	X	X	X	X	X	X	X	X	X	X
Body weight ^e	X	X			X		X	X		X	X		X		X	X	X	X	X	X
Vital signs: blood pressure/pulse rate ^f	X	X			X		X	X		X	X		X		X	X	X	X	X	X
ECG (12-lead local)	X																			
Diabetes and nutrition counseling ^g		X																		
Transfer to insulin lispro ^h		X																		
Transfer to allowed study basal insulin regimen ⁱ		X																		
Basal and prandial insulin dose assessment ^j		X	X	X	X	X	X	X	X	X	X	X	X	X	X	X	X	X		
Titrate basal insulin ^j		X	X	X	X	X	X													
Titrate prandial doses (as needed) ^k								X	X	X	X	X	X	X						

Study Procedure	Study Screening	Lead-In Period						Intensive Titration Period								Maintenance Period			Safety Follow-Up	ED
		2	3a	4a	5	6a	7	Treatment Period								16	17	18		
eCRF Visit Number	1	2	3a	4a	5	6a	7	8	9a	10	11	12a	13	14a	15	16	17	18	801	ED ^b
Visit Window (± days)		3	3	3	3	3	3	4	3	3	7	7	7	7	7	7	7	7	7	
Time on Study Relative to First Active Treatment Dose (weeks)	-9	-8	-7	-6	-4	-2	-1	0	1	2	4	6	8	10	12	18	22	26	30	
Ancillary Supplies/Diaries/IP																				
Dispense blood glucose meter, monitoring and ancillary supplies and complete training ^{l,m}		X						X		X	X		X		X	X	X	X		
Distribute study diary		X			X		X	X		X	X		X		X	X	X	X		
Diary use training ^m		X																		
Collect study diary and transfer diary data to eCRF (InForm) ⁿ					X		X	X		X	X		X		X	X	X	X	X	X
Train on collecting 4-point and 10-point SMBG Profile ⁿ		X																		
Review 4-point SMBG profiles ^o			X	X	X	X	X	X	X	X	X	X	X	X	X	X	X	X	X	X
Remind patient of 10-point SMBG requirements ^p						X	X							X			X			
Review 10-point SMBG profiles								X							X			X		X ^q
Review/discuss hypo data			X	X	X	X	X	X	X	X	X	X	X	X	X	X	X	X		X
Dispense IP		X			X			X			X		X		X	X	X			
Patient returns used and unused study drug supplies					X			X			X		X		X	X	X	X		X
Drug accountability					X			X			X		X		X	X	X	X		X

Study Procedure	Study Screening	Lead-In Period						Intensive Titration Period								Maintenance Period			Safety Follow-Up	ED
		2	3a	4a	5	6a	7	Treatment Period								16	17	18		

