9.1.4.2. Ten-Point Self-Monitoring Blood Glucose

Patients in both study arms should be instructed to perform 10-point SMBG profiles prior to 3 visits during the study (Visits 8, 15, and 18). Three 10-point profiles should be done during the 2 weeks prior to each visit. Each 10-point profile during this 2-week time interval should be completed over a 1-day period, preferably on 3 nonconsecutive days (weekdays and weekends), as per the Schedule of Activities (Section 2). The 10-point profile consists of 10 SMBG measurements on the same day at premeal, 1-hour, and 2-hours after the start of the morning, midday, and evening meals, and at bedtime. The 10-point SMBG profile is inclusive of the daily 4-point SMBG readings. Patients should be encouraged to eat a morning, midday, and evening meal on the days that the 10-point SMBG is monitored. Premeal measurements should be taken before the patient begins eating the meal. Patients may eat a snack and cover with bolus insulin if that is their usual practice. Missing values in 10-point SMBG profiles will not be considered protocol deviations unless, in the opinion of the investigator, they are excessive and reflect noncompliance with the protocol.

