Baseline is defined as the last nonmissing measurement at or before the randomization visit (Visit 8) unless otherwise specified.

A restricted maximum likelihood-based, mixed-effect model repeated measure (MMRM) analysis will be used to analyze continuous longitudinal variables. All the longitudinal observations at each scheduled postbaseline visit will be included in the analysis. The model for the analysis of the primary efficacy endpoint of change from baseline in HbA1c will include the fixed class effects of treatment, strata (country, type of basal insulin, and number of prandial doses at entry), visit, and treatment-by-visit interaction, as well as the continuous, fixed covariate of baseline value. For analyses of variables other than HbA1c, the HbA1c stratum ($\leq 8.5\%$, $> 8.5\%$) will be included in the model. An unstructured covariance structure will be used to model the within-patient errors. Significance tests will be based on least squares (LS) means and Type III tests. If this analysis fails to converge, the following covariance structures will be tested in order:

- Toeplitz with heterogeneity
- Autoregressive with heterogeneity
- Compound symmetry with heterogeneous variances
- Toeplitz
- Autoregressive
- Compound symmetry without heterogeneous variances

The first covariance structure that converges will be used. The Kenward-Roger approximation will be used to estimate denominator degrees of freedom.

An analysis of covariance (ANCOVA) will also be used to analyze continuous variables. The model for the change from baseline to the Week 26 HbA1c endpoint will include treatment and strata (country, type of basal insulin, and number of prandial doses at entry) as fixed effects and baseline as a covariate. Unless otherwise stated, missing endpoints will be imputed using the last-observation-carried-forward (LOCF) approach, using only postbaseline data. For analyses of variables other than HbA1c, the HbA1c stratum ($\leq 8.5\%$, $> 8.5\%$) will be included in the model.

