### 6.10. Concomitant and Prior Therapy

Concomitant medication will be summarized and compared between treatment groups using Fisher's exact test for the Randomized Population during the treatment period. The percentages of patients receiving each concomitant medication will be summarized by treatment using PT nested within Anatomical Therapeutic Chemical (ATC) Level 3 code. Medications will be ordered by decreasing frequency within ATC level. Concomitant medication used during the lead-in period will also be summarized for the Enrolled Population.

A summary of previous diabetes therapies that were discontinued prior to informed consent will be generated for the Enrolled Population.

Total daily basal and total daily prandial insulin doses for the day prior to Visit 2 will be entered into the eCRF. The daily basal doses and individual prandial insulin doses (that is, morning meal, midday meal, evening meal, bedtime/snack/other) will be entered into eCRF after Visit 2. At a given visit, total daily basal insulin dose to be used for analysis will be calculated as the

mean of the total daily basal insulin doses on the 3 days prior to the visit date (or the days between the previous visit date and the current visit date if the number of days between the 2 visit dates is <3). Similarly, the dose for each meal will be calculated as the mean of the doses on the 3 days prior to the visit date (or the days between the previous visit date and the current visit date, whichever smaller). Total daily prandial insulin dose to be used for analysis will be calculated as the sum of the individual meal insulin doses. If either total daily basal insulin dose or total daily prandial insulin dose is missing, total daily insulin dose and prandial/total insulin dose ratio will be set as missing for analysis.

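### SAP Table 6.2 gives the insulin-dose MMRM the visit list of the 10-point SMBG profiles, so patients who stop IP before Week 12 have no record in the only model SAP 6.11.5 names for dose

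*SAP*

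**What the plan says.** SAP Table 6.2 has a single treatment-period row labelled "10-point SMBG, basal, prandial insulin doses, prandial/total insulin dose ratios". Total dose is not named in the label. The population is "All Randomized Patients with a baseline and at least one post-baseline observation", and baseline is Visit 8. The post-baseline cell has two parts: a by-visit list, "Visits , 15, and 18 prior to discontinuation of IP", and a last-value endpoint, "Last of Visits 9-18 prior to discontinuation of IP".

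The dose data are much denser than that list:
- The Protocol's Schedule of Activities marks "Basal and prandial insulin dose assessment" at every visit from 2 to 18.
- SAP 6.10 has daily basal and individual prandial doses entered in the eCRF after Visit 2. It derives a value per visit: "the dose for each meal will be calculated as the mean of the doses on the 3 days prior to the visit date", with a parallel rule for basal dose.
- The lead-in dose row of Table 6.2 uses every visit from 3 to 8.

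On the model, Protocol 10.3.3.2 assigns basal, prandial and total dose and the prandial/total ratio to the MMRM of Section 10.3.1, which states: "All the longitudinal observations at each scheduled postbaseline visit will be included in the analysis". SAP 6.11.5 likewise names an MMRM for these endpoints and no other model. SAP 6.3 says in general terms that an ANCOVA with LOCF will also be used for continuous variables.

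**The concern.** The visit list matches the schedule of the 10-point profiles, which Protocol 9.1.4.2 places before Visits 8, 15 and 18. It does not match the dose schedule. Ten scheduled dose visits follow randomization (Visits 9 to 18), and the row names two of them. The SAP gives no reason for analysing fewer dose visits than Protocol 10.3.1 requires.

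Change in dose at Week 26 is a listed secondary objective. With only Visits 15 (Week 12) and 18 (Week 26) in the model, a patient who stops IP before Week 12 has a baseline but no post-baseline record, and so is excluded. For a patient who stops between Weeks 12 and 26, the only post-baseline value informing Week 26 is Week 12, together with baseline and strata. SAP 6.3 rests the MMRM on missing at random. The doses left out, from Weeks 1 to 10 and Weeks 18 and 22, are observed values that would help to make that assumption credible. Weeks 1 to 10 fall in the period when prandial insulin is intensively titrated.

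**Working it through.** **Plan's own figures (SAP 5.2).** Inputs: margin 0.4, true difference 0, SD 1.1, 320 and 160 completers, two-sided 95% CI.
- SE = 1.1 × √(1/320 + 1/160) = 0.1065.
- Power = Φ(0.4/0.1065 − 1.96) = Φ(1.796) = 0.964, against 96% stated.
- 480/0.85 = 564.7, against about 564 stated.

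Both reproduce, and neither depends on this point. The documents give no figure for the dose analysis.

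**Patients with no record in the dose MMRM.** Inputs: N = 564 and 15% dropout over 26 weeks (SAP 5.2); Visit 15 at Week 12, Visit 11 at Week 4 and Visit 9 at Week 1 (Schedule of Activities). Assumptions: the 15% is read as IP discontinuation and visits fall at their nominal weeks. The documents do not give dropout timing, so two patterns are shown.

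| First post-baseline visit in model | Constant hazard: 564 × (1 − 0.85^(w/26)) | Linear: 564 × 0.15 × w/26 |
|---|---|---|
| Visit 15 (w = 12), as printed | 40.8 (7.2%) | 39.0 (6.9%) |
| Visit 11 (w = 4), if that number was lost | 13.9 | 13.0 |
| Visit 9 (w = 1), all dose visits | 3.5 (0.6%) | 3.3 |

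- Using all dose visits recovers about 40.8 − 3.5 = 37 patients (constant hazard).
- The limits for the printed list are 0 (all dropout after Week 12) and 564 × 0.15 = 84.6 (all before).
- For total dropout of 5%, 10% and 20%, the constant-hazard counts are about 13, 27 and 55.

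**Precision (illustration with assumed values).** Take serial correlation ρ^(weeks apart) with ρ = 0.95 to 0.98 per week, and 15% dropout uniform over 26 weeks. The variance of the Week 26 mean is the last diagonal element of the inverse of Σ p_k V_k⁻¹. Here p_k is the share of patients whose last visit in the model is the k-th, and V_k is the covariance of the visits up to it. The ratio of the two-visit to the ten-visit variance is 1.025 (ρ = 0.95) to 1.041 (ρ = 0.98). The standard error is therefore larger by a factor of √1.025 = 1.012 to √1.041 = 1.020, or 1% to 2%.

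**Bias (illustration with assumed values).** Simulations took a dose-change SD of 20 U, about 15% dropout, and a hazard multiplied by e^0.8 per SD of the last recorded dose change.
- One arm with a true mean change of 12.0 U: the two-visit model gives 11.1 U and the all-visit model 12.0 U.
- Two arms with true means 12 and 10 U, the same dropout mechanism in each and weekly correlation 0.97: the two-visit means are 11.2 and 9.2 U. The difference before rounding is 1.98 U, against a true 2.0 U.

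The arm means shift, but the comparison barely moves.

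**The case against.** **The other half of the cell.** A reader might infer that early leavers drop out of the secondary objective altogether. The documents do not support that. The same cell adds "Last of Visits 9-18 prior to discontinuation of IP", so a patient who stops at Week 8 with on-IP dose values enters a last-value analysis, and SAP 6.3 provides an ANCOVA with LOCF for continuous variables in general. This objection stands, and it confines the point to the MMRM. It does not remove it: SAP 6.11.5 and Protocol 10.3.3.2 name only the MMRM for dose, and a last-value endpoint does not replace that model.

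**The gap before the comma.** A visit number may have been lost, so the list cannot be called certainly two visits, and the gap itself is not an error in the plan. This also stands. But one lost number would give three of ten dose visits, which still falls short of Protocol 10.3.1. If the number were Visit 11, as in the 1,5-AG row, about 13 to 14 patients would still have no record.

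**Bias.** A reader might take the shift in an arm mean as bias in the treatment effect. The objective compares arms, and under a common dropout mechanism the shift essentially cancels. Nothing in the documents links dropout to dose or suggests that any such link differs by arm.

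**Importance.** Dose lies outside the multiplicity scheme (SAP 6.5), and the precision loss is small. Both are true. They limit the weight of the point, but they give no reason to leave the SAP at odds with the Protocol.

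**Conclusion.** The point holds as a mismatch between the SAP and the Protocol on a listed secondary objective. Table 6.2 gives insulin dose the SMBG visit list, while the Schedule of Activities, SAP 6.10 and Protocol 10.3.1 and 10.3.3.2 all point to the full set of scheduled dose visits.

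Its size is modest. About 39 to 41 of 564 patients (7%) would have no record in the dose MMRM, given 15% IP discontinuation spread over the 26 weeks; 0 to about 85 is possible under other timing. Under the assumed correlations, the variance of the Week 26 mean is 2.5% to 4% higher. The missing-at-random basis is weaker because observed doses are left out. Bias in the treatment difference would need dose-related dropout that differs by arm, which is neither shown nor implied by the documents. HbA1c non-inferiority, its 96% power and the sample size do not change.

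**What to change.** In SAP Table 6.2, split the row:
- Keep the SMBG visits for 10-point SMBG.
- Give basal, prandial and total insulin dose and the prandial/total ratio their own row, with Visits 9 through 18 prior to discontinuation of IP as the post-baseline visits for the MMRM. This also brings total dose into the table.
- If the unstructured covariance does not converge, use the fallback order already set out in SAP 6.11.1.

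In SAP 6.11.5, state whether the ANCOVA on the last of Visits 9 to 18 is run for dose and, if so, that it supports the MMRM.

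The cost is SAP wording and some programming on data that the eCRF already holds; no new collection is needed. The one downside is a larger covariance matrix: ten visits give 10 × 11/2 = 55 unstructured parameters, against 3 for two visits, so the fallback order is more likely to be needed.

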**Baseline and Post-Baseline Definitions and Patient Population by Study Period and Type of Analysis**

Study Period/Analysis	Patient Population	Baseline Observations	Post-Baseline Observations
1,5-AG	All Randomized Patients with a baseline and at least one post-baseline observation	Visit 8 prior to initiation of IP	Visits 11, 15, and 18 prior to discontinuation of IP AND Last of Visits 9-18 prior to discontinuation of IP

Health outcomes: ITSQ, EQ-5D-5L, EQ- VAS, WPAI-GH	All Randomized Patients with a baseline and a post- baseline observation	Last of Visits 1-8	Last of Visits 9-18 prior to discontinuation of IP
Safety Laboratory Tests (chemistry, hematology, lipids) – continuous analysis	All Patients in the Safety Population with a baseline and a post-baseline observation	Last of Visit 1-8	Visit 18 (planned) AND last of Visits 9-18 (planned including early discontinuation visits) regardless of IP use
Safety Laboratory Tests (chemistry, hematology, lipids) – categorical analysis	All Patients in the Safety Population with a normal baseline (with respect to the direction being analyzed) and a post- baseline observation	Visits 1-8 (including unplanned tests)	Visits 9-18 (including unplanned tests) regardless of IP use
TEAEs	All Patients in the Safety Population	Prior to first dose of randomized IP (or Visit 8 date if the dose date is missing) but after the first dose of open-label insulin lispro in the Lead-in Period	From first dose of randomized IP to last dose of randomized IP AND From first dose of randomized IP to Visit 801
Hypoglycemia events	Safety Population	All Visits 2-8	All Visits 9-18 prior to discontinuation of IP
Weight and vital signs	All Patients in the Safety Population with a baseline and a post-baseline observation	Last of Visits 2-8	Visits 9-18 prior to discontinuation of IP AND Visits 9-801 regardless of IP use
Anti-insulin lispro antibodies	Safety Population	Visit 2	Visits 3-801 regardless of IP use

Abbreviations: 1,5-AG = 1,5-Anhydroglucitol; ANCOVA = analysis of covariance; EQ-5D-5L = European Quality of Life - 5 Dimensions 5 Level; EQ-VAS = EuroQol visual analogue scale; HbA1c = hemoglobin A1c; IP = investigational product; ITSQ = Insulin Treatment Satisfaction Questionnaire; ITT = intention-to-treat; LOCF – last-observation-carried forward; MMTT = mixed meal tolerance test; MMRM = mixed-effect model repeated measures; PPG = postprandial glucose; SMBG = self-monitored blood glucose; TEAE = treatment-emergent adverse event; WPAI-GH = Work Productivity and Activity Impairment General Health.

## 6.2. Adjustments for Covariates

Stratification factors of this study include country (China vs. Other), HbA1c stratum at baseline ( $\leq 8.5\%$  vs.  $>8.5\%$ ), type of basal insulin during the lead-in period (glargine U-100 vs. degludec U-100), and number of prandial doses at study entry ( $<3$  vs.  $\geq 3$ ).

For the primary analysis of HbA1c, the stratification factor of HbA1c stratum (baseline) will not be included. Instead, the continuous value of baseline (Visit 8) HbA1c will be included in the analysis models.

Other efficacy analyses and safety analysis will include the stratification factors as noted in Sections [6.11](#) and [6.12](#).

### **6.3. Handling of Dropouts or Missing Data**

The analyses for the primary and multiplicity adjusted objectives will be performed with MMRM analysis including all data collected prior to permanent discontinuation of IP through Week 26.

Missing data will be addressed by using a mixed-effect model repeated measures (MMRM) analysis for continuous longitudinal variables. The MMRM model provides consistent estimator when data is missing at random. The model implicitly adjusts for missing data through a variance-covariance structure. An ANCOVA model will also be used to analyze continuous variables. Unless otherwise stated, missing endpoints will be imputed using the last-observation carried forward (LOCF) approach, using only postbaseline data, in the ANCOVA model.

### **6.4. Multicenter Studies**

I8B-FH-ITSE is a multi-country, multi-site study. Site will not be analysed as a fixed effect in any of the models so pooling strategies will not be required.

China level reports of selected enrollment, baseline, efficacy and safety data may also be produced, as applicable.

Summary results for Argentina and Mexico may produced per country specific regulatory requirement.

### **6.5. Multiple Comparisons/Multiplicity**

A graphical approach for multiple comparisons will be used to strongly control the overall Type I error (2-sided alpha level of 0.05) for testing the treatment effect for the primary and the multiplicity adjusted objectives given in Section 4. See Section [6.11.2](#) for the details of graphical testing scheme.

No multiplicity test adjustment will be made for other objectives.

### **6.6. Patient Disposition**

Frequency counts and percentages of all randomized patients completing and discontinuing from the study will be presented for each treatment group. Reasons for discontinuation from the study and study treatment during the 26-week treatment period will be compared between treatment groups using Fisher's exact test. Reasons for discontinuation from the study at Visit 801 will be summarized by the randomized treatment groups.

Frequency counts and percentages of all patients entered, enrolled, and discontinued from the study during the lead-in period will be summarized. Reasons for discontinuation during

screening will be summarized for all entered patients. Reasons for discontinuation from the study during the lead-in period will be summarized for all enrolled patients.

Time to all-cause discontinuation (discontinuation for any reason) from the study and from study treatment will be compared between treatment groups for the 26-week Treatment Period. The Kaplan-Meier product limit method will be used to create survival curves and the log-rank test will be used for the treatment comparisons. Time to all-cause discontinuation is defined as the total number of days between the randomization date (Visit 8 date) and date of discontinuation plus 1. Patients who complete the treatment period will be treated as censored using the total number of days between the randomization date and the Visit 18 date plus 1. If sufficient numbers of patients discontinue the study because of AE, similar analysis will be performed for time to discontinuation due to AE.

A listing of the primary reason for treatment discontinuation (if applicable) and study discontinuation will be generated for the Enrolled Population.

Patient allocation by investigator, grouped by country, will be summarized indicating the number of patients who enter the study, the number of patients who participate in the lead-in period, the number of patients who are randomized to study treatment, and the number of patients who discontinue the study during the 26-Week treatment period.

A listing of the randomization treatment assignment will be generated for all randomized patients.

A listing with all the entered subjects indicating entered, enrolled, randomized, safety, completer of treatment, completer of study, per protocol will be provided.

